7. EXPLORATORY OUTCOMES

7.1 COMPARISON TO HISTORICAL DATA

Comparison of NORTH ATRT patients to historical control will be outlined in a separate document. This will be attached as an appendix to this SAP once complete.

8. MISSING DATA

The number of patients with missing disease response/imaging at each timepoint will be listed by disease strata and any reasons provided listed.

Last patient contact and timepoint censored will be summarised and listed for patients.

9. LISTINGS, TABLES AND FIGURES

9.1. LIST OF LISTINGS

Listing 1	Listing of patient and disease characteristics at baseline
Listing 2	Listing of protocol deviations by strata
Listing 3	Concomitant Medication

9.2. LIST OF TABLES

Table 1	Patient recruitment and screening
Table 2	Disease Characteristics at Baseline
Table 3	Patient Characteristics at Baseline
Table 4	Summary of treatment courses and follow up completed.
Table 5	Number of patients completed each course by disease strata
Table 6	Panobinostat Dosing by disease strata
Table 7	Panobinostat Compliance by disease strata
Table 8	Primary Outcome: Event free Survival
Table 9	Primary Outcome: Overall Survival
Table 10	Adverse Event Summary
Table 11	Dose Limiting Toxicities
Table 12	Secondary Outcome: Clinical Benefit Rate
Table 13	Missing data
Table 14	Censored Table

APPENDIX A. EXAMPLE TABLES AND FIGURES

Listing 1: Patient and disease characteristics at baseline

2
3
4
5
6
7
8
9
10
11
12
13
14
15
16
17
18
19
20
21
22
23
24
25

Table 1- Patient recruitment

Disease Type

Trial Stage		MRT/ ATRT	Neuroblastoma [†]	Osteosarcoma [†]
Consented	n	n	n	
Screen fail	n	n	n	
Enrolled	n	n	n	
Number completed full treatment course (12 cycles)				
Completed full follow-up (2 years post end of treatment)	n	n	n	
[†] The osteosarcoma and neuroblastoma arms were closed to recruitment prior to the initial efficacy analysis due to Panobinostat supply	n	n	n	

Table 2 – Disease Characteristics at Baseline

Disease	MRT/ATRT	Malignant Rhabdoid Tumor (MRT)	Atypical Teratoid Rhabdoid Tumor (ATRT)	Osteosarcoma	Neuroblastoma
---------	----------	--------------------------------	---	--------------	---------------

Event	n	n	n	n	n
	Newly Diagnosed n(%)	Newly Diagnosed n(%)	Newly Diagnosed n(%)	Un-resectable lesion n(%)	Refractory n(%)
Relapse no.	Relapsed n(%)	Relapsed n(%)	Relapsed n(%)	Relapsed n(%)	Relapsed n(%)
	1 n(%)	1 n(%)	1 n(%)	1 n(%)	1 n(%)
Status	2 n(%)	2 n(%)	2 n(%)	2 n(%)	2 n(%)
	3 n(%)	3 n(%)	3 n(%)	3 n(%)	3 n(%)
	4 n(%)	4 n(%)	4 n(%)	4 n(%)	4 n(%)
	SD (%)	CR (n%)	SD (%)	SD (%)	SD (%)
CNS involvement n(%)		n(%)	n(%)	n(%)	n(%)
CR n(%)		CR n(%)	CR n(%)	CR n(%)	CR n(%)
Best Response	SD n(%)	SD n(%)	SD n(%)	SD n(%)	SD n(%)
	PR n(%)	PR n(%)	PR n(%)	PR n(%)n(%)	PR n(%)
Surgery n(%)		n(%)	n(%)	n(%)	n(%)
Chemotherapy n(%)		n(%)	n(%)	n(%)	n(%)
RT	RT n(%)	Brain or skull n(%)	Brain or skull n(%)	Brain or skull n(%)	Brain or skull n(%)
	Spine n(%)	Spine n(%)	Spine n(%)	Spine n(%)	Spine n(%)
RT	Chest/thorax n(%)	Chest/thorax n(%)	Chest/thorax n(%)	Chest/thorax n(%)	Chest/thorax n(%)
	Abdomen n(%)	Abdomen n(%)	Abdomen n(%)	Abdomen n(%)	Abdomen n(%)
	Tibia n(%)	Tibia n(%)	Tibia n(%)	Tibia n(%)	Tibia n(%)
	RT Total Dose (Gy) mean(min-max)	mean(min-max)	mean(min-max)	mean(min-max)	mean(min-max)
BMT/PBSC n(%)		BMT/PBSC n(%)	BMT/PBSC n(%)	BMT/PBSC n(%)	BMT/PBSC n(%)
Other treatment		Other (list) n(%)	Other (list) n(%)	Other (list) n(%)	Other (list) n(%)

Complete Response (CR), Stable Disease (SD), Central Nervous System (CNS), Radiotherapy (RT), RT Total Dose (mean, range), Bone Marrow Transplant (BMT), Peripheral blood stem cells (PBSC)

Table 3 – Patient Characteristics at Baseline

Disease MRT/ATRT Tumor (MRT) (ATRT)	Malignant Rhabdoid		Atypical Teratoid Rhabdoid Tumor		X,X
	mean (min-max)	mean (min-max)	mean (min-max)	mean (min-max)	
Osteosarcoma	Male n(%) Female n(%)	Male n(%) Female n(%)	Male n(%) Female n(%)	Male n(%) Female n(%)	X,X
Neuroblastoma	Asian n(%) Black n(%) Caucasian n(%) Unknown n(%) Other n(%)	Asian n(%) Black n(%) Caucasian n(%) Unknown n(%) Other n(%)	Asian n(%) Black n(%) Caucasian n(%) Unknown n(%) Other n(%)	Asian n(%) Black n(%) Caucasian n(%) Unknown n(%) Other n(%)	X,X
Age					
Sex					
Ethnicity					
	Neither Aboriginal or Torres Strait Islander	Neither Aboriginal or Torres Strait Islander			
	Neither Aboriginal or Torres Strait Islander n(%)	Neither Aboriginal or Torres Strait Islander n(%)			
	Both Aboriginal or Torres Strait Islander n(%)	Both Aboriginal or Torres Strait Islander n(%)	Both Aboriginal or Torres Strait Islander		
	Aboriginal n(%)	Aboriginal n(%)	Aboriginal n(%)		Aboriginal n(%)
	Torres Strait Islander n(%)	Torres Strait Islander Unknown n(%)	Torres Strait Islander Unknown n(%)		Torres Strait Islander n(%)
Indigenous status	Unknown n(%)		Unknown n(%)		
Performance Score	mean (min-max)	mean (min-max)	mean (min-max)	mean (min-max)	X,X

Performance Score (Karnofsky ≥ 16 years old, Lansky < 16 years old). Neuroblastoma n=2, numbers reported.

Listing 2: List of protocol deviations, by site.

Site	Deviation	Timepoint	Date
x	x	x	x

Table 4 – Summary of treatment courses and follow up completed.

	MRT/ATRT	Osteosarcoma	Neuroblastoma
Number of completed courses of treatment	mean(min-max)	mean(min-max)	X,X
Time in Follow Up (weeks)	mean(min-max)	mean(min-max)	
Mean and range (min-max)			X,X

Table 5 – Number of patients completed each course by disease strata.

	Number of Patients who completed Course (28 days)			Number of Early	Early Termination
	MRT/ATRT	Osteosarcoma	Neuroblastoma		
MRT/ATRT	n	n	n	n	x
Osteosarcoma	n	n	n	n	x
Neuroblastoma	n	n	n	n	x
Terminations	n	n	n	n	x
Reason	n	n	n	n	x
Course 1	n	n	n	n	x
Course 2	n	n	n	n	x
Course 3	n	n	n	n	x
Course 4	n	n	n	n	x
Course 5	n	n	n	n	x
Course 6	n	n	n	n	x
Course 7	n	n	n	n	x
Course 8	n	n	n	n	x
Course 9					
Course 10					
Course 11					
Course 12					

Table 6 – Panobinostat Dosing by Course and Disease strata

Patient Dosing (mg/m ²)			
	MRT/ATRT	Osteosarcoma	Neuroblastoma
Course 1	mean(minmax)	mean(minmax)	X,X
Course 2	mean(minmax)	mean(minmax)	X,X
Course 3	mean(minmax)	mean(minmax)	X,X
Course 4	mean(minmax)	mean(minmax)	X,X
Course 5	mean(minmax)	mean(minmax)	X,X
Course 6	mean(minmax)	mean(minmax)	X,X
Course 7	mean(minmax)	mean(minmax)	X,X
Course 8	mean(minmax)	mean(minmax)	X,X
Course 9	mean(minmax)	mean(minmax)	X,X
Course 10	mean(minmax)	mean(minmax)	X,X
Course 11	mean(minmax)	mean(minmax)	X,X
Course 12	mean(minmax)	mean(minmax)	X,X

Table 7 – Panobinostat Compliance by Course and Disease strata

	Dose (mg/m ²)	Days Compliant	Total Days
MRT/ATRT	mean(min-max)	mean(min-max)	mean(min-max)
Osteosarcoma	mean(min-max)	mean(min-max)	mean(min-max)
	X, X	X, X	X, X

Neuroblastoma

Mean and range (min-max)

Listing 3: Concomitant Medication

Sorted by disease strata.

Disease Strata	Medication Name	Medication Reason
MRT/ATRT	X	X

MRT/ATRT	x	x
MRT/ATRT	x	x
Osteosarcoma	x	x
Osteosarcoma	x	x
Osteosarcoma	x	x
Neuroblastoma	x	x
Neuroblastoma	x	x
Neuroblastoma	x	x

Table 8 - Primary Endpoint: Event Free Survival**Primary Outcome- EFS**

MRT/ATRT	Osteosarcoma	Neuroblastoma
$x(95\%CI)$	$x(95\%CI)$	x
$x(min-max)$	$x(min-max)$	NA
$x(95\%CI)$	$x(95\%CI)$	x
$x(min-max)$	$x(min-max)$	NA
Proportion (95%CI)		
Proportion(95%CI)		
Proportion(95%CI)		

Overall EFS (95%CI)

Median EFS, months (95%CI)

Sensitivity Analysis - Composite Strategy

Overall EFS (95%CI)

Median EFS, months (95%CI)

Subgroup AnalysisAge at enrolment (<36 months vs. ≥ 36 months)

Radiation therapy (RT vs. no RT)

Up to 2 years post study enrolment

Table 9: Primary Endpoint: Overall Survival**Primary Outcome- Overall Survival**

MRT/ATRT Osteosarcoma Neuroblastoma

Disease status

	$x(95\%CI)$	$x(95\%CI)$	
Overall Survival (95%CI)			
Median overall survival, months (95%CI)			
Number of deaths	n	n	n
Subgroup Analysis			
Age at enrolment (<36 months vs. ≥ 36 months)	$Proportion (95\%CI)$	$Proportion (95\%CI)$	
Radiation therapy (RT vs. no RT)	$Proportion (95\%CI)$		
Disease Status	$Proportion (95\%CI)$		
Up to 2 years post study enrolment			

Table 10 - Treatment-Related Adverse Events

Treatment-Related Adverse Events

Toxicity (CTCAE v4.0)

	Any Grade	Event				
		Grade 1	Grade 2	Grade 3	Grade 4	event
Grade 4	$n(\%)$	n	n	n	n	event
event	$n(\%)$	n	n	n	n	event
event	$n(\%)$	n	n	n	n	event
event	$n(\%)$	n	n	n	n	event
event	$n(\%)$	n	n	n	n	event

Table 11 – Dose Limiting Toxicities

Dose Limiting Toxicity Adverse Events

Toxicity (CTCAE v4.0)

Grade	Frequency
1	n
2	n
3	n
4	n

Grade Frequency
event event event event**Table 12**- Secondary Outcome: Clinical Benefit Rate

Secondary Outcome- Clinical Benefit Rate

MRT/ATRT	Osteosarcoma	Neuroblastoma	
$x(95\%CI)$	$x(95\%CI)$	x	

CBR at 6 months %(95%CI)

CBR at 12 months %(95%CI)

Sensitivity Analysis - Composite Strategy

CBR at 6 months %(95%CI)

CBR at 12 months %(95%CI)

Table 13 -Missing Data

Disease Strata	Missing Outcome Data	
	Data Missing	Reason missing
MRT/ATRT	Disease Assessment	Scan not performed (n)
Osteosarcoma	Lesions not measured on scan (n)	
Neuroblastoma		Other reasons (n)

Table 14 -Censored table

Study ID	Last patient contact (Timepoint)	Censored (Y/N)
1	Week 6	Y
2	Follow-up	N

STATISTICAL REPORT

Final Audit Report

2025-01-06

Created: 2025-01-06

By: [name] ([contact])

Status: Signed

Transaction ID: CBJCHBCAABAAW_WVYuYZRonABUXmlJo-ObbJ8Z7yT7TD

"STATISTICAL REPORT" History

 Document created by [name] ([contact])

2025-01-06 - 5:02:51 AM GMT- IP address: [name]

 Document emailed to A/[name] ([contact]) for signature 2025-01-06

- 5:02:57 AM GMT

 Email viewed by A/[name] ([contact])

2025-01-06 - 5:07:30 AM GMT- IP address: [name]

 Document e-signed by A/[name] ([contact])

Signature Date: 2025-01-06 - 5:48:15 AM GMT - Time Source: server- IP address: [name]

 Agreement completed.

2025-01-06 - 5:48:15 AM GMT

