The final dose per strata was the level where continuous dosing was maintained for a 4-week period with acceptable toxicity and biological effect. The final Panobinostat doses were 6mg/m² per day for the ATRT/MRT cohort, 8mg/m² per day for the neuroblastoma cohort, and 4mg/m² per day for the osteosarcoma cohort.

Study Expansion

The study employed a Simon two-stage minimax design (1). At trial design stage an initial efficacy analysis was planned when a minimum of 9 patients in each strata were enrolled. The regimen would be considered worthy of further study if disease stability at 4 months was observed in 3 or more of the first 9 patients in a stratum and less than 30% of patients experience a DLT at the final dose level. If this was achieved, recruitment would proceed to a total of 20 patients in each strata.

However, due to uncertainty of panobinostat supply, a decision was made to permanently close the osteosarcoma and neuroblastoma arms prior to the initial efficacy analysis when 9 and 2 had been enrolled in the osteosarcoma and neuroblastoma arms, respectively. At that time, it was decided to continue recruitment into the ATRT/MRT cohort who had met the initial efficacy criteria for 3/9 participants with disease stability and <30% experiencing a DLT at the final dose level. The ATRT/MRT arm closed in December 2021 due to termination of the study supply agreement, at that time 14 participants had been enrolled in the ATRT/MRT arm.

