5. ANALYSIS OF THE PRIMARY OUTCOME(S)

5.1. MAIN ANALYSIS

5.1.1. Event free survival

Primary Estimand

Population: All patients eligible and enrolled into trial with MRT/ATRT (strata 1), osteosarcoma (strata 2), or neuroblastoma (strata 3).

Treatment: Panobinostat

Outcome: Estimated 2-year Event free survival (EFS). EFS is calculated as the time from study enrolment to first documented disease progression, relapse or second malignancy, or death from any cause up to 2 years after study enrolment. The latest possible time of risk being 2 years after enrolment, or the last date known alive.

Summary measure: The probability of EFS (Kaplan-Meier) at with 95%CI will be estimated each stratum*. Kaplan- Meier curves will be plotted for EFS probability, enrolment date as start of risk period. Median EFS time will be calculated at 2 years post-enrolment.

**only calculated if stratum had adequate sample size (osteosarcoma and ATRT/MRT only).*

Subgroup Analysis:

Descriptive statistics (proportions) by subgroup for each disease strata.

Age at enrolment <36 months (3 years old) vs. ≥36 months

Radiation therapy (RT) vs. no RT

Disease status at trial entry (complete response vs stable disease)

Intercurrent Events

Potential intercurrent events:

Patient comes off study or treatment due to toxicity before an event is observed. Patient comes off study or treatment to receive another treatment.

Strategy for handling intercurrent event:

Treatment policy

EFS will be estimated for patients regardless of early treatment or trial termination. This approach assumes that data collected is reflective of those missing data (patients who withdrew from trial).

Sensitivity Analysis

Composite Strategy

Patients coming off study or protocol treatment due to an irreversible or unacceptable dose limiting toxicity or a Serious adverse event (SAE) before an event is observed, will be handled by the composite strategy. The removal from study/treatment date will be treated as an event.

Patients coming off study or protocol treatment to receive another treatment will also be handled by this strategy in the same analysis.

Primary Estimand Calculation

EFS will be estimated and visualised using the Stata sts list and graph commands.

```
stset tvar, fail(event) origin(time enrol_date) enter(time consent_date)
sts list, strata(disease type) risk table(6 12 24) sts graph, strata(disease type) risk
table(0 6 12 18 24) xlabel(0 6 12 18 24) tmax(24) Median EFS will be estimated

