using Stata stsum command stsum, by(disease type)
```

Subgroup analysis

The proportion in each group and 95%CI will be estimated using Stata's *ci proportions* command.

Sensitivity analysis (as above with alternate event) *stset tvar, fail(event_comp) origin(time enrol_date) enter(time consent_date)*

Where time is in months and patients will be censored at their last known contact alive.

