5.1.2. Overall survival

Primary Estimand

Population: All patients eligible and enrolled into trial with MRT/ATRT (strata 1), osteosarcoma (strata 2), or neuroblastoma (strata 3).

Treatment: Panobinostat, dosing as per protocol.

Outcome: Estimated Overall Survival (OS). OS is calculated as the time from study enrolment to death from any cause.

Summary measure: The OS probability (Kaplan-Meier) and 95%CI will be estimated for each stratum* up to 2 years post-enrolment. Kaplan-Meier curves will be plotted for OS probability; enrolment date as start of risk period. The number of deaths and the median OS time will be reported up to 2 years post-enrolment.

**only calculated if stratum had adequate sample size (osteosarcoma and ATRT/MRT only).*

Subgroup Analysis:

As per section 5.1.1

Intercurrent Events

Potential intercurrent events:

Patient comes off study due to toxicity, or to start a new treatment.

Strategy for handling intercurrent event:

Patients coming off study due to a related toxicity or to start a new treatment will be handled with the treatment policy. OS will be analysed for all patients regardless of treatment received until last study visit.

Sensitivity Analysis

Composite Strategy

Patients coming off study due to toxicity or to start a new treatment before death could be observed will be handled by the composite strategy. The removal from study date will be treated as an event/death in sensitivity analysis.

Estimand Calculation

OS will be estimated and visualised using the Stata sts list and graph commands.

stset tvar, fail(death) origin(time enrol_date) enter(time consent_date) sts list,

strata(disease type)

sts graph, strata(disease type) tmax(24)

Median OS will be estimated using Stata stsum command *stsum,*

by(disease type)

Where time is in months and patients will be censored at their last known contact alive.

5.1.3 -Safety

Adverse events will be summarised by grade and type defined by CTCAE Version 4 from 1 week to 12 months after intervention commencement.

Relationship to study drug (definite, probable, possible) adverse events summarised in a table, with the worst AE grade reported by each participant.

A summary table of Dose Limiting Toxicities will include AE type, grade, and frequency.

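### Table 8 labels the median EFS with a 95% CI but its cells hold a minimum-maximum, and the SAP names no confidence-interval method for a median

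*SAP*

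**What the plan says.** SAP section 5.1.1 gives the EFS probability an interval: "The probability of EFS (Kaplan-Meier) at with 95%CI will be estimated each stratum". For the median it says only "Median EFS time will be calculated at 2 years post-enrolment", with no interval. The calculation paragraph of that section obtains the median "using Stata stsum command stsum, by(disease type"), and section 5.1.2 does the same for survival: "Median OS will be estimated using Stata stsum command". No other command for a median, and no method for its confidence limits, appears in the SAP.

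The table shells in Appendix A do expect an interval. Table 8 carries the row label "Median EFS, months (95%CI") twice, once for the main analysis and once for the composite strategy. Table 9 carries "Median overall survival, months (95%CI"). In Table 8, however, two rows of cells read x(min-max) for MRT/ATRT and osteosarcoma and NA for neuroblastoma.

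The stratum sizes are in section 2: for MRT/ATRT, "at that time 14 participants had been enrolled in the ATRT/MRT arm"; the other two arms closed "when 9 and 2 had been enrolled in the osteosarcoma and neuroblastoma arms, respectively".

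**The concern.** A minimum-maximum describes how far individual times spread. A confidence interval describes how precisely the median is known. They answer different questions and usually differ in width. With censoring, the largest observed time may also be the end of a patient's follow-up and not an event.

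If a range is printed under a 95% CI label, the reader cannot tell that it is a range and will take the median to be less precisely estimated than it is. This would happen in the results table of a primary endpoint, in both the main and the sensitivity block. The body text would not stop it, because it does not say how an interval for a median is to be computed.

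**Working it through.** The SAP states no figure for the median or its limits, so there is nothing to reproduce. The check has three parts.

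**1. Matching labels to cells in Table 8.** The text extraction separated labels from cells, but each kept its order.

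| Row | Label | Cells, MRT/ATRT and osteosarcoma | Neuroblastoma |
|---|---|---|---|
| 1 | Overall EFS (95% CI) | x(95%CI) | x |
| 2 | Median EFS (95% CI) | x(min-max) | NA |
| 3 | Composite: overall EFS (95% CI) | x(95%CI) | x |
| 4 | Composite: median EFS (95% CI) | x(min-max) | NA |
| 5 to 7 | Three subgroups | Proportion (95% CI) | none shown |

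Seven labels face seven rows of cells. The third subgroup label, disease status, has slipped below the title of Table 9, but section 5.1.1 lists three subgroups. NA in rows 2 and 4 is what one would expect for a median in a stratum of two patients. No label in Table 8 asks for a range, so the conflict does not depend on layout. The footnotes to Tables 4 and 7 explain min-max as the range, so in this SAP it does not mean confidence limits.

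**2. Exact coverage, no censoring.** Inputs: n = 14 and n = 9 from section 2, with all enrolled patients analysed. The range misses the true median only if all n times fall on the same side of it:

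coverage = 1 − 2 × 0.5^n

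- n = 14: 1 − 2/16384 = 0.9999, or 99.99%
- n = 9: 1 − 2/512 = 0.9961, or 99.6%

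For comparison, the interval from the l-th to the u-th ordered time covers the median with probability Σ C(n,k) 0.5^n over k = l, …, u − 1.

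- n = 14: 4th to 11th time, 94.3%; 3rd to 12th, 98.7%
- n = 9: 2nd to 8th time, 96.1%

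**3. Size in months, by simulation.** Assumptions, not in the SAP: exponential EFS, true median of 4, 6 or 12 months, and censoring only at 24 months (section 5.1.1 ends the risk period at 2 years). There were 3000 samples per setting. The interval is the Kaplan-Meier log-log 95% CI for the median. Entries are medians over samples, and an unreached upper limit counts as infinite.

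| n | True median | 95% CI for the median | Min-max | Upper limit not reached |
|---|---|---|---|---|
| 14 | 4 | 1.2 to 7.8 | 0.3 to 17.3 | 0% |
| 14 | 6 | 1.8 to 11.8 | 0.4 to 24.0 | 1% |
| 14 | 12 | 3.6 to 23.4 | 0.9 to 24.0 | 47% |
| 9 | 4 | 0.5 to 9.9 | 0.5 to 14.9 | 1% |
| 9 | 6 | 0.6 to 14.8 | 0.6 to 22.4 | 10% |
| 9 | 12 | 1.3 to not reached | 1.3 to 24.0 | 70% |

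Widths at n = 14:

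- median 4: 17.3 − 0.3 = 17.0 against 7.8 − 1.2 = 6.6, a ratio of 2.6
- median 6: 24.0 − 0.4 = 23.6 against 11.8 − 1.8 = 10.0, a ratio of 2.4
- median 12: 24.0 − 0.9 = 23.1 against 23.4 − 3.6 = 19.8, a ratio of 1.2

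**The case against.** The best defence is that Appendix A holds example shells. All three median rows in Tables 8 and 9 are labelled with a 95% CI, so a confidence interval is evidently intended. The min-max looks like a placeholder carried over from the descriptive tables, and a careful programmer would notice. This stands as far as it goes: a wrong interval is possible, not certain. It does not remove the conflict between label and cell, which sections 5.1.1 and 5.1.2 leave unresolved.

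A reader might also infer more than the documents support:

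- *That the primary result itself would carry the wrong interval.* Section 2.2.1 makes the 2-year EFS the primary endpoint. Its row in Table 8 has a 95% CI in both label and cells. The median is a further summary of that endpoint.
- *That the plan can yield no interval except the range.* Section 5.1.1 orders Kaplan-Meier probabilities with 95% CIs, and an analyst could read limits for the median from these at 0.5. The plan does not direct this, but it does not prevent it. That stsum prints quartiles without confidence limits is general knowledge of the software and is not stated in the SAP. The mismatch stands without it.
- *That the range would usually end at the 24-month cap.* Under the same model, the probability that the largest time is 24 months is 1 − (1 − S(24))^n. With a 6-month median, S(24) = 0.5^4 = 0.0625, which gives 60% at n = 14 and 44% at n = 9. With a 4-month median, S(24) = 0.5^6 = 0.0156, which gives 20% and 13%. So it depends on the median.
- *That Table 9 has the same error.* It shows no min-max cell. For OS only the interval method is missing.

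**Conclusion.** The point holds as an inconsistency in a table shell, together with an unstated method. Four cells in Table 8 ask for a range where their labels promise a 95% CI, and neither section 5.1.1 nor section 5.1.2 says how an interval for a median is to be obtained.

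Filled as drawn, the printed interval would cover the median almost surely and not at about 95%. At n = 14 it would be about 2.4 to 2.6 times as wide as a proper interval if the true median is 4 to 6 months, but only about 1.2 times as wide at 12 months. At n = 9 the typical lower ends coincide and the difference lies in the upper end. The coverage figures assume no censoring. The figures in months rest on the exponential model and the assumed medians. Earlier censoring would change them.

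The point is minor: it concerns a supporting summary and does not touch the EFS probability. It is still worth correcting before the tables are produced.

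**What to change.** - In Table 8, change the four median cells (main and composite rows, MRT/ATRT and osteosarcoma) to x(95%CI).
- In sections 5.1.1 and 5.1.2, name a Kaplan-Meier based confidence interval for the median, for example Stata's stci by disease type, and state the transformation used. Tables 8 and 9 can then be filled as labelled.
- State that a median or limit that cannot be estimated is reported as not reached. At these stratum sizes this may be common for the upper limit if the median is long.
- If a range is also wanted, give it a row of its own, labelled as the range of observed times, with censored values marked.

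The cost is one command, a sentence in each of two sections and four table cells. It needs no new data and changes no other analysis.
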